6.5.2 Prohibited Concomitant Therapy

Receipt of any exclusionary treatments or medications prior to screening will be assessed at screening to determine eligibility as described in the exclusion criteria.

The following medications are prohibited during this study, unless clinically indicated to prevent/treat progression of disease (as described above):

- Small -molecule tyrosine kinase inhibitors, including JAK inhibitors (e.g., baricitinib, ibrutinib, acalabrutinib, imatinib, gefitinib).
- Monoclonal antibodies targeting cytokines (e.g., TNF inhibitors, anti-IL-1 [e.g., anakinra, canakinumab], anti-IL-6 [e.g., tocilizumab, sarilumab, siltukimab]), or T-cells (e.g., abatacept).

The following medications are prohibited at any time during this study:

- GM-CSF agents (e.g., sargramostim).
- Lenzilumab outside of this trial (currently not available, but in case it becomes available during the study).
- Other immunosuppressants which, in the judgment of the investigator, pose risk of immunosuppression in combination with lenzilumab that is larger than the risk of COVID-19.
- Chloroquine or hydroxychloroquine use for the treatment of COVID-19.

Chloroquine antagonizes remdesivir in a dose dependent manner as evidenced by an increase in the median effective dose (EC50) for remdesivir with increasing chloroquine concentration. Another *in vitro* study found that chloroquine induces a dose dependent inhibition of the formation of the active nucleoside triphosphate metabolite of remdesivir. Thus, chloroquine or hydroxychloroquine use for the treatment of COVID-19 is prohibited during the study.

Concomitant use of any other experimental treatment or off-label use of marketed medications intended as specific treatment for COVID-19 or SARS-CoV-2 infection, and not specified in local written guidelines or the NIH COVID-19 Treatment Guidelines are prohibited.

Overall, the risk of potential drug-drug interactions between lenzilumab and concomitant medications is low. As a monoclonal antibody, lenzilumab is not expected to undergo metabolism by hepatic enzymes or renal elimination. Drug interactions between lenzilumab and substrates/inhibitors/inducers of drug metabolizing enzymes are not expected.

6.5.3 Rescue Medicine

Not Applicable

6.5.4 Non-Research Standard of Care

Not Applicable

7. STUDY INTERVENTION DISCONTINUATION AND SUBJECT DISCONTINUATION/WITHDRAWAL

7.1 Halting Criteria and Discontinuation of Study Intervention

7.1.1 Individual Infusion Halting

See [Section 6.1.4](#) for information about dosing modifications due to laboratory abnormalities.

For an individual subject, an individual infusion must be stopped if they have a suspected drug-related event of hypersensitivity (Grade 2 or higher) during the infusion. While there are no criteria for grading “hypersensitivity” in the Division of AIDS (DAIDS) Table for Grading the Severity of Adverse Events,[\(14\)](#) sites should use Acute Allergic Reaction from that toxicity table. Subjects who have an IV infusion stopped for a safety related issues will not continue with dosing.

The treatment of any given subject may be stopped for SAEs, clinically significant AEs, severe laboratory abnormalities, or any other medical conditions that indicate to the site Investigator that continued dosing is not in the best interest of the patient.

In addition, a subject in this clinical study may discontinue study drug at their request for any reason. Every effort should be made to encourage subjects to remain in the study for the duration of their planned outcome assessments. Subjects should be educated on the continued scientific importance of their data, even if they discontinue study drug.

Unless the subject withdraws consent, those who discontinue study drug early will remain in the study. The reason for subject discontinuation of study drug should be documented in the case report form.

7.1.2 Study Halting

Given the potential severity of COVID-19, there are no pre-specified study stopping rules. Instead there will be close oversight by the protocol team and frequent DSMB reviews of the safety data.

7.2 Withdrawal from the Study

See Section 7.2 of the Master protocol document.

7.3 Readmission

See Section 7.3 of the Master protocol document.

7.4 Lost to Follow-Up

See Section 7.4 of the Master protocol document.

8. STUDY ASSESSMENTS AND PROCEDURES

8.1 Screening and Efficacy Assessments

8.1.1 Screening Procedures

Screening procedures may be done from Day -1 to Day 1 (Day 1 is the calendar day of randomization). However, in many cases all the screening assessments can be done in less than 24 hours. If that is the case, Day 1 pre-study product administration baseline assessments, specimen collection and the initial study product administration can occur on the same calendar day as the screening procedures.

After the informed consent, the following assessments are performed to determine eligibility:

- Confirm the positive SARS-CoV-2 test result (per inclusion criteria).
- Confirm that patient does not have a positive influenza test during the current illness for which they are being screened. (Influenza testing is not required per protocol.)

- Take a focused medical history, including the following information:
 - Day of onset of COVID-19 signs and symptoms.
 - Prior enrollment in ACTIV-5 or BET.
 - History of vaccinations within 4 weeks prior to screening, including SARS-CoV-2 vaccination.
 - Exclusionary vaccine history includes any live vaccine (that is, live attenuated) within 4 weeks prior to screening.
 - History of chronic medical conditions, including chronic oxygen requirement and/or use of CPAP or BiPAP at home, prior to onset of COVID-19.
 - History of medication allergies.
 - Medications and therapies for this current COVID-19 illness and history of any medication listed in the exclusion criteria. Site should identify if the patient received any steroids in the 7 days prior to randomization.
 - Ask if the patient is participating in another clinical trial or plans to enroll in another clinical trial in the next 30 days.
- Women of childbearing potential must agree to either abstinence or use at least one acceptable method of contraception from the time of screening through 5 months post study IP dosing.*

**Note: Acceptable methods include barrier contraceptives (condoms or diaphragm) with spermicide, intrauterine devices (IUDs), hormonal contraceptives, oral contraceptive pills, and surgical sterilization.*
- Targeted physical examination (targeted exam details in MOP).
- Height and weight (height can be self-reported).
- Assess need for supplemental oxygen, mechanical ventilation, or ECMO.
- Blood for screening laboratory evaluations, if not done as part of routine clinical care in the preceding 48 hours, should be collected to evaluate the following parameters:
 - ALT
 - AST
 - Serum creatinine (and calculate eGFR)
 - Any automated calculation by the clinical laboratory or published formula for this calculation is acceptable. The site should select a formula to be used for all subjects enrolled at the site for the duration of the study.
- Urine or serum pregnancy test (in women of childbearing potential).

Clinical screening laboratory evaluations will be performed locally by the site laboratory. A screening lab (i.e., from the hematology and chemistry laboratory panels) may be repeated once if, in the opinion of the investigator, the laboratory abnormality is due to an intercurrent transient condition or it is an aberrant laboratory value. The overall eligibility of the subject to participate in the study will be assessed once all screening values are available. If performed just prior to randomization, data obtained from screening can also be a baseline assessment of severity and efficacy.

Study subjects who qualify will be randomized in the interactive response technology system (IRT) system, and all others will be registered as screen failures only in the EDC system. The ordinal scale should be done at the time of randomization; the site will need this data to randomize the subject. Clinical laboratory tests performed as part of routine clinical care in the 48 hours prior to enrollment will be accepted for determination of eligibility.

8.1.2 Efficacy Assessments

For all baseline assessments and follow-up visits, refer to the Schedule of Assessments (SOA) for procedures to be completed, and details below for each assessment.

Laboratory tests performed as part of routine clinical care in the 24 hours prior to first dose will be accepted for the baseline laboratory tests. Baseline may be the same as the screening laboratory tests if obtained in the 24 hours prior to first dose.

8.1.2.1 Measures of Clinical Support, Limitations and Infection Control

The subject's clinical status will be captured on each study day while hospitalized up until and including Day 29. Once subjects are discharged from the hospital, they will have a study visit on Days 8, 15, 22, 29, and 60 visits (only the ordinal score will be obtained on Day 60) as an outpatient. The Day 8, Day 22 and Day 60 visits do not have laboratory tests or collection of samples and may be conducted by phone. Day 15 and 29 visits are preferred to be in person in order to collect safety laboratory testing, stored samples, and virologic assessments but may be performed by phone. Clinical status is largely measured by the ordinal scale. The ordinal scale can also be evaluated over the phone if the discharged subject is unable to return for in-person visits on Day 15 and 29.

Ideally, the ordinal scale is completed concurrently with the NEW Score just prior to study product administration. The following measures are recorded for the ordinal scale. See MOP for more detailed description of ventilatory devices in each category:

- Hospitalization.
- Oxygen requirement.
- Non-invasive mechanical ventilation (via mask) requirement.
- High-flow oxygen requirement.
- Invasive mechanical ventilation (via endotracheal tube or tracheostomy tube) requirement.
- ECMO requirement.
- Ongoing medical care preventing hospital discharge (COVID-19 related or other medical conditions).
- Limitations of physical activity (self-assessed and reported as new or increased limitations as compared to status prior to the onset of COVID-19)).
- Isolated for infection control purposes.

8.1.2.2 Ordinal Scale

The ordinal scale is the primary measure of clinical outcome per the Master protocol document (Section 8.1.1.1)

8.1.3 Exploratory Assessments

See Section 8.1.2 of the Master protocol document. Additional exploratory assessments include:

- Qualitative and quantitative polymerase chain reaction (PCR) for SARS-CoV-2 in OP swab on Day 1; Days 3, 5, 8, and 11 (while hospitalized); and Days 15 and 29 (if attends in-person visit or still hospitalized).
- Qualitative and quantitative PCR for SARS-CoV-2 in blood on Day 1; Days 3, 5, 8, and 11 (while hospitalized).
- Plasma proteomic analysis of cytokines and markers of inflammation including GM-CSF, MCP-1, IP-10, IL-6, IL-1, TNF-a, G-CSF, and MIPa on Days 1, 3, 8, 15, and 29 (if attends in-person visit or still hospitalized).
- Blood RNA transcriptome analysis on Days 1, 3, 8, 15, and 29 (if attends in-person visit or still hospitalized).
- PBMC assessment for phenotype and functional reactivity on Days 1, 3, 8, 15, and 29 (if attends in-person visit or still hospitalized; collected only at sites capable of collecting and processing PBMC).
- Serum samples for PK (at pre-dose, Day 5 (if hospitalized), Day 15, and Day 29).

8.2 Safety and Other Assessments

Safety procedures and assessments are described in Section 8.2 of the Master protocol document. The total volume of blood collected over the course of this study for safety and research evaluations (including samples for secondary research-defined in master protocol 10.1.1.2) is approximately 450 mL, with a maximum daily volume of approximately 73 mL.

8.3 Adverse Events and Serious Adverse Events

AE reporting will occur as described in Section 8.3 of the Master protocol document.

9. STATISTICAL CONSIDERATIONS

See Section 9 of Master protocol document. However, there are important differences between BET-B and the Master protocol, and these are presented here.

While the endpoints are ordered differently and BET-B's primary analysis, and some secondary analyses, are limited to a pre-specified subgroup, all BET stages will analyze the same endpoints. Furthermore, the method of analysis for any given endpoint will be conducted the same for BET-B as for the other interventions.

Several statistical features were modified at the time BET-B was changed to a Phase 2/3 design including an increase in sample size, change to the primary endpoint, and new futility analysis.

Statistical Hypotheses

The primary null hypothesis being tested is that incidence the composite endpoint of mechanical ventilation or death is the same between the experimental and control arms within the following subgroup of (subjects with baseline CRP<150 mg/L, ordinal score<7, and age<85). The parameter estimated by the primary analysis is the odds ratio.

These differences are study adaptations that were implemented mid-study. The changes were motivated entirely by the results of the LIVE-AIR study. Adapting BET-B to a Phase 2/3 trial was deemed a timely approach for replication of the LIVE-AIR results. At the time of this adaptation, the BET team involved in this decision had no knowledge of interim BET-B results broken down by active versus placebo groups.

9.1 Sample Size Determination

The LIVE-AIR trial estimated a HR of about 1.5 in its overall population, and a HR of above 3 in the identified subgroup. The corresponding relative risks for the primary endpoint were in the 2.5 or 2.6 range, and the corresponding odds ratio were around 3. Because the treatment effect in the post hoc subgroup may be overly optimistic, the BET-B updated sample size assumes an intermediate odds ratio of 2.5 for the subgroup. The LIVE-AIR trial also observed a 21% event rate in the placebo group in the subgroup, which is likely higher than expected in this trial. (The primary analysis, logistic regression, will estimate an odds ratio. For the expected range of control event rates, the relative risk of 2.2 corresponds to an odds ratio of about 2.5; the relevant observed odds ratios in LIVE-AIR were about 3.)

A sample size of 400 in the subgroup will yield 80% power if the control event rate is 16% and 89% power if the control rate is 21%, if the odds ratio is 2.5 and a two-sided alpha=.049. (An odds ratio of 2.5 is defined such that if the control event rate is 16%, the treated rate would be 7%). At most 550 participants (that is, subjects randomized into BET-B and relevant shared controls) will be randomized. Based on early BET baseline estimates, roughly 75% of subjects are expected to fall in the primary analysis subgroup at baseline (CRP<150, age<85, and OS<7). The trial will enroll subjects until 400 are randomized in the subgroup or 550 overall, whatever comes first. These calculations are not inflated for missing data, as little missing data are expected.

9.2 Statistical Analyses

9.2.1 General Approach

The general approach follows the corresponding section in the Master Protocol (Section 9.3.1) with the following exception:

The adapted study is now a Phase 2/3 double-blind, placebo- controlled, randomized trial testing a superiority hypothesis where the intervention will be considered statistically significant if the final two-sided p-value is < .05. The statements of declaring agents “promising” for a p-value <.20 as noted in the Master protocol are not applicable to BET-B. Only 95% confidence intervals will be computed for the treatment effect corresponding to the primary and key secondary endpoints.

Because of an interim analysis completed after 100 total subjects tested the original primary endpoint (Day 8 Ordinal Score) at $\alpha=.001$, the primary analysis will be conducted at $\alpha=.049$, for an overall two-sided .05 type I error rate (using a Bonferroni approach to multiplicity.)

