3. OBJECTIVES AND ENDPOINTS

Table 4. BET-B Study Objectives

OBJECTIVES	ENDPOINTS (OUTCOME MEASURES)
Primary	
To evaluate the clinical efficacy of lenzilumab as assessed by survival without mechanical ventilation through Day 29 in subjects with ordinal scores 5 or 6 at baseline with a CRP<150 mg/L and age<85 years.	Occurrence of mechanical ventilation or death at any point through Day 29 in subjects with ordinal scores 5 or 6 at baseline with a CRP<150 mg/L at baseline and age<85 years, where the event is one of these two categories: 7. Hospitalized, on invasive mechanical ventilation or extracorporeal membrane oxygenation (ECMO);

OBJECTIVES	ENDPOINTS (OUTCOME MEASURES)
	8. Death.
Key Secondary (in order of testing)*	

To evaluate the clinical efficacy of lenzilumab as assessed by:
 
 1. Survival without mechanical ventilation through Day 29 in subjects with ordinal scores 5 or 6 at baseline with a CRP<150 mg/L and age<85 years. 	
Time to ventilation or death Day 29 in subjects with ordinal scores 5 or 6 at baseline with a CRP<150 mg/L at baseline and age<85 years, where the event is one of these two categories:
 
 7. Hospitalized, on invasive mechanical ventilation or extracorporeal membrane oxygenation (ECMO); 8. Death.

 2. Time to sustained recovery compared to the control arm in subjects with ordinal scores 5 or 6 at baseline with a CRP<150 mg/L and age<85 years. 	
Day of recovery is defined as the first day on which the subject satisfies 1 of the following 3 categories from the ordinal scale (and does not return to a score of 4 or higher for the remainder of the study period):
 
 1. Not hospitalized, no new or increased** limitations on activities; 2. Not hospitalized, but new or increased limitation on activities and/or requiring new or increased home oxygen, CPAP, or BiPAP; 3. Hospitalized, not requiring new or increased supplemental oxygen - no longer requires ongoing medical care.

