
 3. Survival without mechanical ventilation through Day 29. 	
Occurrence of mechanical ventilation or death at any point through Day 29, where the event is one of these two categories:
 
 7. Hospitalized, on invasive mechanical ventilation or ECMO (OS5 or 6 only); 8. Death. 
In those subjects who are at ordinal score 7 at baseline, the event is defined as death through Day 29.

OBJECTIVES	ENDPOINTS (OUTCOME MEASURES)
4. Time to sustained recovery	
Day of recovery is defined as the first day on which the subject satisfies 1 of the following 3 categories from the ordinal scale (and does not return to a score of 4 or higher for the remainder of the study period):
 
 1. Not hospitalized, no new or increased limitations on activities; 2. Not hospitalized, but new or increased limitation on activities and/or requiring new or increased home oxygen, CPAP, or BiPAP; 3. Hospitalized, not requiring new or increased supplemental oxygen - no longer requires ongoing medical care.
Other Secondary	

1. To evaluate the clinical efficacy of lenzilumab as compared to the control arm as assessed by:
 
 ○ Ordinal scale: 
 ▪ Clinical status using ordinal scale at Days 8, 15, and 29. ▪ Time to an improvement of one category and two categories from Day 1 (baseline) using an ordinal scale. ▪ Mean change in the ordinal score from Day 1 to Days 3, 5, 8, 11, 15, 22, and 29. 	
 ● Clinical outcome assessed using ordinal scale daily while hospitalized and on Days 8, 15, 22, and 29.

 ○ Oxygenation: 
 ▪ Supplemental oxygen use up to Day 29. 	
 ● Days of supplemental oxygen (if applicable) up to Day 29.

 ○ Non-invasive ventilation/high-flow oxygen: 
 ▪ Non-invasive ventilation/high-flow oxygen use up to Day 29. ▪ Incidence and duration of new non-invasive ventilation or high-flow oxygen use through Day 29. 	
 ● Days of non-invasive ventilation/high-flow oxygen (if applicable) up to Day 29.
○ Invasive mechanical ventilation/	

OBJECTIVES	ENDPOINTS (OUTCOME MEASURES)

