9.2.4 Hierarchical Testing

This protocol contains three key secondary endpoints. The key secondary endpoints will be tested in the order presented in the endpoint section. If the primary analysis is significant at .049, then the first key secondary endpoint can be tested at .049. If this is significant, then the second key secondary endpoint can be tested at .049, and so forth. There is no hierarchical testing for other (non-key) secondary endpoints.

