## 6.8. Multiple Comparisons/Multiplicity

This protocol contains four key secondary endpoints. The key secondary endpoints will be tested in the order presented in the endpoint section using the following hierarchical hypothesis testing: If the primary analysis is significant at .049, then the first key secondary endpoint can be tested at .049. If this is significant, then the second key secondary endpoint can be tested at .049, and so forth. There is no hierarchical testing for other (non-key) secondary endpoints.

The supplementary analyses (e.g., Westfall-Young and Hochberg) in Section 6.8 of the master SAP were intended for the proof-of-concept trials and thus will not be conducted for the BET-B study.

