## 8. EFFICACY EVALUATION

For this phase 2/3 double-blind placebo controlled randomized trial two-sided p-value < 0.049 will be considered statistically significant at the final analysis. That is, an interim efficacy analysis done with alpha=.001, leads to alpha=.049 at the final test, using a Bonferroni approach to yield an overall .05 type I error rate. It is noted that since the endpoint and population are different between the interim test and final test, common interim analysis testing approaches such as O'Brien-Fleming would not apply, hence the use of Bonferroni which will be slightly conservative.

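### Protocol 9.2.1 sets the final success threshold at p < .05, but the plan's final alpha is .049; the count of key secondary endpoints and one age limit also need correcting

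*Protocol*

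**What the plan says.** **Success threshold.** The General Approach section of the protocol (9.2.1) states that "the intervention will be considered statistically significant if the final two-sided p-value is < .05". Its next paragraph explains that an interim analysis of the original primary endpoint (Day 8 ordinal score), after 100 subjects, used alpha .001. The primary analysis is therefore run at .049 "for an overall two-sided .05 type I error rate", by Bonferroni. Protocol 9.1 gives power "if the odds ratio is 2.5 and a two-sided alpha=.049", and Protocol 9.2.4 uses .049 at each step of the hierarchy. SAP 5, the text of SAP 6.6 and SAP 6.8 also use .049. SAP 8 states the rule outright: "two-sided p-value < 0.049 will be considered statistically significant at the final analysis".

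**Number of key secondary endpoints.** Protocol 9.2.4 says "This protocol contains three key secondary endpoints" and takes their order from the endpoint section. In that section, Table 4 has a block that begins "Key Secondary (in order of testing" and numbers four items, the last being "4. Time to sustained recovery". SAP 6.8 says "This protocol contains four key secondary endpoints".

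**Age limit.** The body of SAP 8.2.2 restricts the second key secondary analysis to subjects aged 85 or younger. Its own heading refers to the primary endpoint subgroup, which is under 85. The same endpoint is defined with age under 85 in Protocol Table 4, in SAP 3.1.2.1, 3.2.2 and Table 1, and in the title of the SAP Table 10 shell.

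**The concern.** The trial was expanded to serve as a confirmatory pivotal study, so its success criterion should appear once, with one value. Protocol 9.2.1 gives two values in consecutive paragraphs. Read literally, the first does not deliver the overall error rate that the second claims. A result with .049 ≤ p < .05 would be a success under the first sentence of 9.2.1 and a failure under SAP 8.

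The other two items are smaller but also touch the tested hierarchy. Taken literally, a count of three leaves it unclear whether the fourth endpoint (sustained recovery in all subjects) is tested with alpha control. A programmer who followed the body of SAP 8.2.2 would admit 85-year-olds to an analysis within that hierarchy.

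**Working it through.** **1. The plan's own alpha split.** Inputs from Protocol 9.2.1: interim alpha .001, final alpha .049, combined by Bonferroni.

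- As planned: .001 + .049 = .050, which is the stated overall level.
- With the printed threshold: .001 + .05 = .051, which exceeds .05 by .001.

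Bonferroni is an upper bound. If the two tests were independent, the overall rates would be 1 − (.999 × .951) = .04995 and 1 − (.999 × .95) = .05095. The printed threshold would exceed .05 in that case as well.

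**2. Width of the disputed zone.** The two-sided critical |z| is 1.9600 at .05 and 1.9686 at .049. Only results between these values are affected.

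**3. Which alpha was powered.** Inputs from Protocol 9.1 and SAP 5: 400 in the subgroup, odds ratio 2.5, control event rate 16% or 21%, stated power 80% and 89% at two-sided .049. *Assumption:* 200 per arm, following the 275/275 overall split in Protocol section 5.

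Treated rate, from treated odds = control odds / 2.5:

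- 16% control: .16/.84 = .1905; divided by 2.5 = .0762; rate = .0762/1.0762 = 7.08%.
- 21% control: .21/.79 = .2658; divided by 2.5 = .1063; rate = .1063/1.1063 = 9.61%.

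Power of an unadjusted two-proportion test with pooled variance under the null, n = 200 per arm:

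Power = Φ{[d − z·√(2·p̄(1−p̄)/n)] / √([p_c(1−p_c) + p_t(1−p_t)]/n)}, where p_c and p_t are the control and treated rates, d = p_c − p_t and p̄ is their mean.

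| Control / treated | Stated, at .049 | Computed at .049 | Computed at .05 | Difference |
|---|---|---|---|---|
| 16% / 7.08% | 80% | 79.72% | 79.96% | 0.24 points |
| 21% / 9.61% | 89% | 88.68% | 88.85% | 0.17 points |

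Unpooled variance gives 80.3% and 89.2% at .049. The stated power reproduces at .049, the alpha that both documents name for it. A difference of about 0.2 points could not by itself show which alpha was used. It does show that stating .049 throughout costs nothing in sample size or power.

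**4. The two clerical items, side by side.**

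- Endpoint count: Protocol 9.2.4 says three. Protocol Table 4 numbers four, SAP 3.1.2.1 and 3.2.2 list four, and SAP 6.8 says four.
- Age limit: the body of SAP 8.2.2 includes age 85. Its heading and every other definition of this endpoint cited above exclude it. The affected set is subjects aged exactly 85 who also have baseline ordinal score 5 or 6 and CRP below 150 mg/L.

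**The case against.** The strongest reply is that the documents already settle the matter. The paragraph after the disputed sentence gives .049 and the reason for it, and SAP 8 states the operative rule without ambiguity. On this view .05 in 9.2.1 is the general significance level, which the next paragraph then divides into .001 and .049. That reading would be acceptable if the sentence spoke of the overall level. It speaks of the final p-value, the quantity that SAP 8 compares with 0.049.

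It is also fair to say that .051 is an upper bound, that SAP 8 itself calls Bonferroni slightly conservative here, and that no inflation follows if the SAP is applied. All of that stands and limits the size of the point. So does the remark that the power figures come from an unadjusted test, whereas the primary analysis is a covariate-adjusted logistic regression with multiple imputation. They serve only to show that nothing else moves.

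On the clerical items, the order and membership of the hierarchy can be recovered from Table 4. The age symbol occurs once and could be an artefact of text conversion, although the CRP inequality on the same line came through correctly. It should be checked against the source file.

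Finally, these edits do not remove every alpha inconsistency. The drift-parameter definition in SAP 6.6 prints alpha as 0.49, a separate slip. The plan also reports 95% intervals beside a .049 test, so in the disputed zone a normal-theory 95% interval could exclude 1 although the test is not significant. Neither observation weakens the point about 9.2.1.

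**Conclusion.** The success sentence in Protocol 9.2.1 is wrong as written. It contradicts the next paragraph and the rest of both documents, and under the plan's own Bonferroni method it totals .051 rather than .05. The consequence is small: at most .001 of excess type I error, and a changed decision only for .049 ≤ p < .05. The sample size and planned power do not depend on the wrong value. The power comparison assumes 200 per arm and an unadjusted test; the alpha sum needs neither assumption.

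The endpoint count and the age symbol are real but clerical. Read together, the documents make the intended rule clear: final alpha .049, four key secondary endpoints, age under 85. The decision rule is therefore not undefined, but a confirmatory plan should have its threshold corrected before unblinding.

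**What to change.** - **Protocol 9.2.1:** change the final threshold from < .05 to < .049, and state that this preserves an overall two-sided level of .05.
- **Protocol 9.2.4:** change the number of key secondary endpoints from three to four.
- **SAP 8.2.2:** change the age limit from ≤ 85 to < 85, after checking the symbol in the source file.

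The cost is three wording edits. The intended analysis, sample size and power do not change, because .049 is already the alpha used for planning and testing.
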